8.4.8. Adverse Events of Special Interest

8.4.8.1. Protocol-defined Adverse Events of Special Interest that Require Reporting to Sponsor's Global Pharmacovigilance

For purposes of this protocol, the following are considered protocol-defined AEs of special interest (PDAESI) to be sent to the Sponsor's Global PV for evaluation:

- PDSS events
- ISRs of pus-containing lesion (abscess, infection, or inflammation), ulceration, necrosis, and atrophy

The process for reporting a protocol-defined adverse event of special interest is the same as that for reporting an SAE (Sections 8.4.6 and 8.4.7), using the same Serious Adverse Event/Protocol-Defined Adverse Events of Special Interest Form. PDAESI to be reported to Global PV can be either serious or nonserious, according to the criteria outlined in Section 8.4.1. PDAESI that occur before trial drug administration do not require reporting to Global PV.

8.4.8.2. Protocol-defined Adverse Events of Special Interest that do not Require Reporting to Sponsor's Global PV

The following are considered PDAESI that do not need to be sent to the Sponsor's Global PV and will be recorded only in the clinical database:

- ISR following sc administration, including, but not limited to, pain, bleeding, tenderness, skin induration, warmth, itching, erythema, inflammation/swelling, rash, skin irritation, dermal irritation, or bruising at the injection site

Pain at the injection site will not be recorded as an AE (but will be captured as a trial safety measure) unless it is different in character, intensity, duration, or frequency from that expected, based on Investigator judgment.

8.4.9. Protocol Deviations Because of an Adverse Event

If a participant experiences an AE or medical emergency, deviations from the protocol may be allowed on a case-by-case basis. To ensure participant safety, after the event has stabilized or treatment has been administered (or both), the Investigator or other physician in attendance must contact the Clinical Leader as soon as possible to discuss the situation. The Investigator, in consultation with the Sponsor, will decide whether the participant should continue to participate in the trial.

8.5. Pregnancy and Postpartum Information

Any female participant becoming pregnant during the trial will discontinue and will be withdrawn from the trial.

All pregnancies of women participating in the trial and female partners of men participating in the trial, if applicable that occur during the trial or within six months from last IMP dose, whichever is longer, are to be reported within 24 hours. The completed Pregnancy Form should be sent to the LSO/CRO (as applicable, for eg, a CRO in a country without a Sponsor LSO); the LSO will forward the report to the Sponsor's Global PV. The process for reporting a pregnancy is the same as that for reporting an SAE but using the Pregnancy Form (Section 8.4.7).

The Investigator is not required to report participants who are found to be pregnant between screening and baseline, provided no protocol related procedures were applied.

Because this IMP(s) has suspected reproductive toxicity, female partners of men participating in the trial who become pregnant will be asked to sign an ICF. All female participants and female partners of men participating in the trial who become pregnant will be monitored for the outcome of the pregnancy (including spontaneous, elective, or voluntary abortion). If the pregnancy continues to term, the outcome (health of the infant up to 8 weeks of age), including details of birth and presence or absence of any birth defect, congenital abnormalities, or maternal and newborn complications, will be reported to the Sponsor. Any complication of pregnancy during the trial and any complication of pregnancy that the Investigator becomes aware of after withdrawal from the trial will be reported as an AE or SAE, as appropriate.

If the pregnancy in the woman participating in the trial and/or the female partners of men participating in the trial does not continue to term, one of the following actions will be taken:

- For a spontaneous abortion, report as an SAE (both Pregnancy and Serious Adverse Event Forms should be completed).
- For an elective abortion due to developmental anomalies, report as an SAE (both Pregnancy and Serious Adverse Event Forms should be completed).
- For an elective abortion **not** due to developmental anomalies, report on the Pregnancy Form; do not report as an AE.

8.6. Clinical Product Complaints

8.6.1. Definition of Clinical Product Complaints

A clinical product complaint is defined as a problem or potential problem with the physical quality or characteristics of clinical IMP supplies (TV-44749 sc formulations and ZYPREXA im) and/or clinical device supplies used in a clinical research trial sponsored by Teva.

Examples of a clinical product complaint include, but are not limited to, the following:

- suspected contamination
- questionable stability (eg, color change, flaking, crumbling)
- defective components
- missing or extra units (eg, primary container is received at the investigational center with more or less than the designated number of units inside)
- incorrect packaging or incorrect or missing labeling/labels
- unexpected or unanticipated taste or odor, or both

Each investigational center will be responsible for detecting, documenting, and reporting a clinical product complaint by completing the Product Complaint Form provided by Teva and emailing it to [contact] as soon as possible after becoming aware of the issue.

Reporting a complaint must not be delayed even if not all the required information can be immediately obtained. Known information must be immediately reported. The Sponsor will collaborate with the Investigator to obtain any outstanding information.

Once the complaint has been investigated by the Sponsor, when required, an event closure letter may be sent to the investigational center where the complaint originated or to all investigational centers using the product.

If the clinical product complaint is related to a device, comparator, co-medication, rescue medication, or any other product planned in the protocol not manufactured by Teva, the complaint will be forwarded to the manufacturer/wholesaler of that product.

8.6.2. Handling the IMP/Devices at the Investigational Center

The Investigator is responsible for retaining the product in question in a location separate from the Investigator's clinical trial supplies. The Sponsor may request that the Investigator return the product for further evaluation and/or analysis. If this is necessary, the clinical trial monitor or designee will provide the information needed for returning the IMP.

If it is determined that the investigational center must return all IMPs, the Sponsor will provide the information needed to handle the return.

8.6.3. Product Complaint Associated with Adverse Events or Serious Adverse Events

If there is an AE or SAE due to product complaint, the protocol should be followed for recording and reporting of the AE or SAE (Section 8.4.2 to Section 8.4.7).

8.7. Pharmacokinetics

8.7.1. Timing of Pharmacokinetic Sampling

Blood samples (3 mL) will be obtained via direct venipuncture or indwelling catheter for the determination of plasma concentration of olanzapine and potentially for olanzapine metabolites at the time points detailed in [Table 1](#) to [Table 5](#).

Specimen collection, processing, and handling requirements are detailed in the Laboratory Manual.

Every effort must be made to obtain the PK samples within the allowed limits for sampling times, as defined in [Table 6](#) and [Table 7](#). The exact time of sample collection must be noted in the source documents and CRF.

When the PK blood sample collection coincides with safety assessments, PK blood samples should be collected as close to the scheduled time point as possible. Assessment of vital signs and ECGs should precede PK blood sampling.

8.7.2. Changes to Pharmacokinetic Sampling Scheme

Not applicable.

8.7.3. Pharmacokinetic Parameters

Pharmacokinetic parameters will be calculated from concentration-time data using noncompartmental methods, when possible.

The following PK parameters will be calculated following ZYPREXA im administration:

- C_{max}
- AUC_{0-t}
- λ_z over the 216-hour period following administration
- [REDACTED]
- [REDACTED]
- [REDACTED]
- [REDACTED]
- [REDACTED]
- [REDACTED]

Additional PK parameters for olanzapine (e.g. [REDACTED], $AUC_{0-\infty}$, etc) may be calculated if deemed necessary.

The following PK parameters will be calculated following sc olanzapine extended-release formulation administration:

- C_{max}
- AUC_{0-t}

- $AUC_{0-\infty}$
- [REDACTED]

Additional PK parameters for olanzapine may be calculated if deemed necessary.

8.8. Pharmacodynamics

Pharmacodynamic parameters are not evaluated in this trial.

8.9. Genetics

8.9.1. Pharmacogenomics

- [REDACTED]

8.10. Biomarkers

- [REDACTED]

8.10.1. Digital Biomarkers

Digital biomarker or outcome measures are not evaluated in this trial.

8.11. Immunogenicity Assessments

Not applicable.

8.12. Medical Resource Utilization and Health Economics

Medical resource utilization and health economics parameters are not evaluated in this trial.

8.13. Total Blood Volume

The total volume of blood to be collected for each participant in this trial is approximately 370 mL (at maximum). The total amount of blood will be drawn over a study duration of approximately 19 weeks.

Additional blood samples for toxicology, PK, and/or biomarkers should be collected in case of severe ISRs (Section 8.3.6); pus-containing lesion (abscess, infection, or inflammation), ulceration, necrosis, or atrophy (Section 8.3.7); or suspected PDSS (Table 8 and Section 8.3.8). Details for all blood volumes and assessments will be included in the Laboratory Manual.

8.14. Assessment of Leakage

Immediately after injection of any of the olanzapine extended-release sc formulations, qualified investigational center personnel will observe the site of injection for the incidence of leakage (ie, to inspect whether the injected suspension appears at the injection site after completion of the injection). The leakage evaluation score will be recorded in the source documents and CRF using the rating scale (0 to 4) as described in Table 13.

Continuous leakage assessment will be performed (ie, additional leakage assessment will be performed for these cohorts after the immediate assessment described above). Specifically, if leakage continues, the evaluation should be continued for up to 10 minutes and the leakage stop time should be recorded. The additional leakage score (0-4) will be recorded at the end of the leakage to capture the total volume of leakage observed post-injection. If leaked IMP is seen at the injection site 10 minutes post-injection, it should be gently wiped, while avoiding pressure or squeezing of the injection site. If leakage does not stop 10 minutes post-dose, record the re-evaluated leakage score, gently wipe the injection site and record 10 minutes for leakage reassessment time (ie, stop time). Whether or not wiping of IMP occurred at 10 minutes post-dose will be recorded on the eCRF as a Yes/No question. In case leakage continues after wiping the site (ie, after 10 minutes), this will also be recorded in the eCRF and the MM should be notified.

A recorded leakage score of 4 should be reported to the MM within 24 hours. Patients with a leakage score of 4 may be replaced.

Table 13: Leakage Evaluation

Appearance	Score
No sign of the injected suspension on the skin	0
Pinpoint to ballpoint size drop is visible on the skin	1
Only a small amount of injected suspension is visible on the skin (ie, most of the injected suspension penetrated the skin)	2
Approximately half of the injected suspension is visible on the skin (ie, approximately half of the injected suspension penetrated the skin)	3
Most of the injectable solution is visible on the skin (ie, little or no injectable solution penetrated the skin)	4

9. STATISTICAL CONSIDERATIONS

This section describes the statistical analysis as foreseen at the time of planning the trial. Changes, additions, and further details about the analyses will be described in the Statistical Analysis Plan (SAP). After finalization of the SAP, any additional analyses or changes to analyses that may be required will be fully disclosed in the CSR.

9.1. Analysis Sets

9.1.1. Enrolled Analysis Set

The enrolled analysis set will include all participants who sign an ICF and are enrolled in the trial. This analysis set will be used for summarizing demography and baseline data.

9.1.2. Pharmacokinetics Analysis Set

The PK analysis set will include all participants who have sufficient data to calculate at least one PK parameter for any of the olanzapine formulations (IM immediate release or sc ER) and have no events of deviations that would affect the calculation of PK parameters. This analysis set will be used for all PK summaries.

A drug metabolism and PK (DMPK) scientist and a clinical pharmacologist will identify each individual participant's PK parameters to be included in the analysis. Individual PK parameters that are considered outliers (eg, parameters that were based on partial data) will be excluded from the primary analysis. Justification for exclusion of parameters will be provided in the PK parameter raw data file provided by DMPK. A Statistical Data Review meeting will be held prior to database lock of the trial (and prior to seeing any data results), and any protocol deviations that could potentially impact the PK will be identified. Data from these participants will also be excluded from the primary and secondary PK analyses. Criteria for exclusion of individual participant data will be defined in the SAP. A leakage score of 4 after TV-44749 sc administration will result in exclusion from the PK analysis set and the participant will be replaced. Data from excluded participants will be included in the relevant listing.

9.1.3. Safety Analysis Set

The safety analysis set will include all participants who receive at least 1 dose of IMP. This analysis set will be used for all safety summaries.

In the safety analysis set, cohorts will be assigned based on the formulation that the participants actually received, regardless of the cohort they were randomized to, unless otherwise specified.

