
To evaluate the overall safety of the trial in participants with schizophrenia or schizoaffective disorder.
	
The safety measures/parameters are:
 
 • Occurrence of adverse events during trial participation (day 1 to day R84) • Change in clinical laboratory (chemistry, hematology) tests, vital sign measurements (body temperature, respiratory rate, pulse rate, and blood pressure) during trial participation (day 1 to day R84) • ECG findings during trial participation (day 1 to day R84) • Use of concomitant medication during trial participation (day 1 to day R84) • Discontinuation for any reason during trial participation (day 1 to day R84) • Discontinuation due to an adverse event during trial participation (day 1 to day R84) 
■ [REDACTED]
 
■ [REDACTED]

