8.4. Adverse Events and Serious Adverse Events

8.4.1. Definitions of Adverse Events and Serious Adverse Events

8.4.1.1. Adverse Events

An AE is any untoward medical occurrence in a participant administered a pharmaceutical product and which does not necessarily have a causal relationship with this treatment.

An AE can, therefore, be any unfavorable and unintended physical sign, symptom, or laboratory parameter that develops or worsens in severity during the course of this trial, or significant worsening of the disease under study, or of any concurrent disease, whether or not considered related to the olanzapine sc formulations or ZYPREXA im.

Accordingly, an AE can include any of the following:

- a new condition or the worsening of a preexisting condition
- intercurrent illnesses
- physical injuries and the mechanism that caused the injury
- events possibly related to concomitant medication
- drug/drug interactions
- events occurring during diagnostic procedures or during any washout phase of this trial
- laboratory or diagnostic test abnormalities

Note: Abnormal laboratory or diagnostic test results at the screening visit that preclude a participant from entering the trial or receiving trial treatment are not considered AEs.

- significant worsening (change in nature, severity, or frequency) of the disease under study or other preexisting conditions (Note: A condition recorded as preexisting that is intermittently symptomatic [eg, headache] and that occurs during this trial should be recorded as an AE).
- events occurring during diagnostic procedures

- laboratory or diagnostic test abnormalities that result in the withdrawal of the participant from the trial, are associated with clinical signs and symptoms or an SAE, require medical treatment or further diagnostic work up, or are considered by the Investigator to be clinically significant
- all events of possible drug-induced liver injury (Section 8.3.4.1.1)
- any physical examination, vital signs measurement, ECG, or other safety assessment finding that is judged by the Investigator as a clinically significant change (worsening) compared with a baseline value

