
To evaluate the safety and tolerability following a single-dose of immediate-release ZYPREXA im in participants with schizophrenia or schizoaffective disorder.
	
The safety and tolerability measures/parameters are:
 
 • Occurrence of adverse events during the 24-hour period following administration of ZYPREXA im (day 4 to day 5) • Change in clinical laboratory (chemistry, hematology) tests, vital sign measurements (body temperature, respiratory rate, pulse rate, and blood pressure) during the 24-hour period following administration of ZYPREXA im (day 4 to day 5) • ECG findings during the 24-hour period following administration of ZYPREXA im (day 4 to day 5) • Use of concomitant medication during the 24-hour period following administration of ZYPREXA im (day 4 to day 5) • Discontinuation for any reason during the 24-hour period following administration of ZYPREXA im (day 4 to day 5) • Discontinuation due to an adverse event during the 24-hour period following administration of ZYPREXA im (day 4 to day 5) • Local tolerability and pain during the 24-hour period following administration of ZYPREXA im (day 4 to day 5) 
[REDACTED]
 
[REDACTED]
 
[REDACTED]

To evaluate the overall safety of the trial in participants with schizophrenia or schizoaffective disorder.
	
The safety measures/parameters are:
 
 • Occurrence of adverse events during trial participation (screening to day R84) • Use of concomitant medication during trial participation (screening to day R84) • Discontinuation for any reason from enrollment until end of trial (day 1 to day R84) • Discontinuation due to an adverse event from enrollment until end of trial (day 1 to day R84) 
[REDACTED]

Statistical Analysis Plan

Pharmacokinetic Trial – Schizophrenia Participants Trial TV44749-NPC-10205

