4.4. Trial Days and Visits

The trial will consist of a screening period (up to 40 days), a 3-day AP washout (WO) period (day 1 to day 3), a 1-day treatment period with immediate-release ZYPREXA im (period 1: day 4), an 8-day follow-up period (period 2: day 5 to day 12) with an optional extension of additional maximum 7 days, a 28-day treatment period with 1 of the 3 extended-release sc olanzapine formulations (period 3: day R1 to day R29), and an up to approximately 8-week follow-up period (day R29 to day R84).

Trial days will be numbered relative to the WO period on day 1 (ie, ..., -2, -1, 1, 2, ...; with day 1 of the washout period of antipsychotics and day -1 being the day before the first day of washout) and the end of the screening period. The trial days will be numbered relative to the TV-44749 administration on day R1 in Period 3 (ie, R1, R2, ...; with day R1 of the TV-44749 administration period and day R29 to day R84 of the follow-up period).

For by visit (time point) summaries, if there are multiple assessments at a post-baseline visit (time point), then the last non-missing assessment at that visit (time point) will be used for the summary (this includes both scheduled and unscheduled assessments). In general, for the by-visit summaries, Early-Termination (ET) visit will be presented as a separate visit, per study periods as follows; if the ET visit occurred between Day 4 to Day R1 (prior to the administration of TV44749) it will be mapped to "ET visit prior to TV44749 administration", if it has occurred between day R1 to day R29 it will be mapped to "ET visit during TV44749 treatment" and in case ET visit has occurred between Day R30 to Day R84 it will be mapped to "ET visit during TV44749 follow-up period". For the 'at any time' summary statistics in the shift tables and in the

presentation of Potentially Clinically Significant (PCS) summaries, all visits will be used (including unscheduled visits).

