7. SAFETY ANALYSIS

7.1. General

The safety analysis set will be used for all safety analyses. Summaries will be presented by cohort and treatment (including any of the IMPs; ZYPREXA im or Olanzapine sc extended-release formulations) and overall, unless otherwise stated.

For continuous variables, descriptive statistics (n, mean, standard deviation, standard error [SE], median, minimum, and maximum) will be provided for actual values and changes from baseline to each time point. For categorical variables, participant counts and percentages will be provided.

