7.2. Adverse Events

Adverse events will be collected and recorded from the time a patient signs the informed consent to the end of follow-up period (day R84).

All adverse events will be coded using the Medical Dictionary for Regulatory Activities (MedDRA). Summaries will be presented for all adverse events occurring after the first dose of IMP (ZYPREXA im and/or Olanzapine extended-released formulation), as overall and by Common Terminology Criteria for Adverse Events [CTCAE] grade, including AEs determined by the investigator to be related to IMP and/or medical device (defined as related or with missing relationship), serious adverse events and injection site adverse events. Adverse events missing relationship to study drug will be included in the study drug related summary. A summary of occurrence of adverse events, serious adverse events and injection site adverse events will be presented separately for period 1 + 2 (from the administration timepoint of Zyprexa IM until and not including the administration timepoint of Olanzapine extended-release formulation), for period 3 (day R1 to day R29) and for the follow up period (day R30 to day R84). The occurrence of adverse events, serious adverse events and injection site adverse events will also be listed for the Wash-Out period (from day 1 to the administration of Zyprexa im). The incidence of adverse events will be summarized using descriptive statistics by SOC and PT. For the incidence of adverse events, patients are counted only once in each SOC category, and only once in each PT category. For the summary by grade, patients are counted at the worst grade.

Protocol defined adverse event of special interest (PDAESI) (section 8.4.8 of the study protocol) will also be summarized and presented by cohort separately for period 1 + 2 (from the administration timepoint of Zyprexa IM until and not including the administration timepoint of Olanzapine extended-release formulation), for period 3 (day R1 to day R29) and for the follow-up period (day R30 to day R84). PDAESI that required reporting to Sponsor's Global PV for evaluation may be presented in a separate summary table.

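### Adverse events of participants who are enrolled but never dosed are left out of the washout listing and the overall adverse-event measure, because all safety analyses use the dosed-only safety set

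*Protocol*

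**What the plan says.** **Population.** Protocol 9.1.3 defines the safety set: "The safety analysis set will include all participants who receive at least 1 dose of IMP". It adds: "This analysis set will be used for all safety summaries". SAP 3.3 gives the same definition. Protocol 9.5 places the safety analyses on this set, and SAP 7.1 says: "The safety analysis set will be used for all safety analyses". Neither document names another population for any adverse-event output.

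**Timing.** Under Protocol Table 1, enrollment is on day 1, the antipsychotic washout covers days 1 to 3, and the first possible IMP dose is ZYPREXA im on day 4. Protocol 5.5 requires an eligibility recheck before that dose.

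**What is meant to be reported.**
- Protocol 8.4.1.1 counts as adverse events "events occurring during diagnostic procedures or during any washout phase of this trial".
- Protocol 8.4.2 and SAP 7.2 collect adverse events from consent.
- The overall-safety objective in Protocol 3.4 includes: "Occurrence of adverse events during trial participation (day 1 to day R84"). SAP 1.4 starts the same measure at screening.
- SAP 7.2 says that adverse events, serious adverse events and injection site events "will also be listed for the Wash-Out period (from day 1 to the administration of Zyprexa im").

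**The concern.** The plan sets out to report adverse events from a period in which nobody has yet received IMP, but draws the reporting population from people who later did. A participant can be enrolled, have an event off medication, then fail the recheck or withdraw, and never receive ZYPREXA im. That person was exposed to a trial procedure and falls within the stated objective, but is outside the set used to report it.

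The omission is selective. The recheck in Protocol 5.5 covers inclusion criteria g and h, and criterion g is clinical stability; an adverse event is also a stated ground for withdrawal in Protocol 7.2. Destabilisation during the washout is therefore a plausible reason for leaving undosed. A washout listing restricted to dosed participants shows those who tolerated the washout well enough to go on. At stake is a complete account of harm during the washout, within an exploratory safety objective.

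**Working it through.** The point rests on setting the population rule against each output it governs. The plan states no figure for it that could be reproduced.

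**Step 1. Follow one participant.** Take someone enrolled on day 1, with an adverse event on day 2, withdrawn on day 3 and given no IMP. This person is in the enrolled set (SAP 3.1) and not in the safety set (SAP 3.3).

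**Step 2. Check each output.**

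| Output | Population and window | Event shown? |
|---|---|---|
| Washout listing (SAP 7.2) | Safety set by the general rule of SAP 7.1; window ends at ZYPREXA im, a time this person does not have | No, as written |
| Overall AE occurrence (Protocol 3.4, SAP 1.4) | Safety set by the same rule; starts on day 1 or at screening | No, as written |
| AE summaries (SAP 7.2) | Events after the first IMP dose | No; washout events are not summarised even for people dosed later |
| Listings of serious events and of events leading to withdrawal (Protocol 9.5) | Treatment-emergent events, defined in Protocol 8.4.2 as after the first dose | No |
| Deaths (Protocol 9.5, SAP 7.3) | Any participant who dies during the trial | Yes, if fatal |
| Disposition (SAP 5.2) | All patients, with reason for withdrawal | Withdrawal and reason only; no AE term, grade or seriousness |

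The first row is decisive. The washout listing is the only planned, unredacted AE output aimed at this period, and it takes the dosed-only population by default. The third row shows that changing the population alone would not be enough for the overall measure, because the summaries also exclude pre-dose events by date.

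**Step 3. Size.** Protocol 9.8 plans about 95 enrolled for about 60 completers. That leaves 95 − 60 = 35 losses over the whole trial, with no split between losses before and after the first dose. The undosed share must therefore be assumed:
- 1% of 95 = 0.01 × 95 = 0.95, about 1 person
- 10% of 95 = 0.10 × 95 = 9.5, about 10 people

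To illustrate, suppose k enrolled participants go undosed, each with a washout event, and everyone else is dosed. Counting only those k people's events, the enrolled set shows k/95 and the safety set shows 0/(95 − k):
- k = 1: 1/95 = 1.1% against 0/94
- k = 3: 3/95 = 3.2% against 0/92
- k = 5: 5/95 = 5.3% against 0/90

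**The case against.** **The exclusion from the listing is inferred.** Protocol 9.1.3 and SAP 3.3 speak of summaries, a listing is not a summary, and SAP 7.2 names no population for the washout listing. Planning a pre-dose listing at all suggests that pre-dose events were meant to appear. Part of this stands: the exclusion follows from a general rule and is not spelled out. But SAP 7.1 and Protocol 9.5 both refer to analyses, and nothing makes an exception for the washout. A programmer following the text would apply the dosed-only flag.

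**A dosed-only set is standard.** This is right for treatment-emergent tables, and nothing here argues against it there.

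**Stronger readings.** A reader might infer more than the documents support:
- *AE discontinuation counted from enrollment is also biased.* SAP 1.4 does list "Discontinuation due to an adverse event from enrollment until end of trial (day 1 to day R84"). However, the disposition summary in SAP 5.2 covers all patients and gives reasons for withdrawal, and SAP 7.6.1 reports failure to complete partly through disposition. An undosed participant who withdrew for an adverse event is counted there.
- *Deaths in the washout disappear.* Both death listings cover anyone who dies during the trial.
- *The early-termination categories need a washout entry.* SAP 4.4 does begin its mapping with "if the ET visit occurred between Day 4 to Day R1 (prior to the administration of TV44749"), but that mapping governs by-visit summaries and not AE listings.
- *The events are lost, or the formulations look safer than they are.* Events are collected from consent, and Protocol 8.4.6 requires serious events to reach the sponsor within 24 hours. Washout events precede every IMP, so no formulation's post-dose results change.

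**Conclusion.** The point holds as a reporting gap. By the stated population rule, adverse events and serious adverse events of participants who are enrolled, affected in the washout and never dosed are left out of the washout listing and the overall AE-occurrence measure. Apart from deaths, no other unredacted AE output shows them.

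The number affected is probably small and is not given in the documents. About 1 to 10 people rests on an assumed undosed share of 1% to 10% of 95, and not all of them need have had an event. The conclusion also rests on reading SAP 7.1 as covering listings, which is the default reading in the absence of another rule. The affected objective is exploratory and descriptive. Data collection, post-dose safety results and PK endpoints are unaffected.

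**What to change.** In SAP 7.1 and 7.2, which prevail over the protocol where the two differ:
- State that the washout AE and SAE listing uses the enrolled analysis set.
- State that the overall AE-occurrence measure uses the enrolled analysis set, with all consented participants for the screening part, and that it includes pre-dose events.
- End the washout window at ZYPREXA im administration, or at withdrawal if no IMP was given.
- Keep the dosed safety set for all treatment-emergent summaries.

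Deaths, the discontinuation measures and the SAP 4.4 mapping need no change.

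The cost is a few sentences in the SAP, a different population flag on one listing, and one descriptive count. The data are already collected. The overall AE count may rise slightly.
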